3 STUDY DESIGN

3.1 OVERALL STUDY CHARACTERISTICS

This is a Phase 2, randomized, open-label 3-arm multicenter study evaluating 12 months of treatment with an LHRHa monotherapy, ARN-509 monotherapy, or the combination in men with non-metastatic biochemically relapsed prostate cancer with rapidly increasing PSA levels after prior definitive therapy for localized prostate cancer. The two experimental arms (ARN-509 monotherapy; ARN-509 + LHRHa) will each be compared with a control arm of standard androgen deprivation (LHRHa monotherapy). Subjects will be stratified by PSADT (< 6 months vs. 6-12 months) and age (≤ 70 vs. greater than 70) and randomized with equal probability (1:1:1 ratio) from within each of the four strata to one of the 3 study arms.

There will be 2 treatment periods of 12 months each (24 months):

- (1) On-therapy Period lasting 12 months, during which time subjects receive randomly assigned protocol therapy
- (2) Off-therapy Observation Period from months 13 through 24

Subjects who develop progressive disease (either by serum PSA or radiographic progression) at any time during the 2 study periods will be removed from the study and will be treated as per individual investigator discretion. Subjects who discontinue before completion of the On-therapy Period in the absence of progressive disease will enter the Off-therapy Observation Period of the study. If subjects do not have evidence of PSA or radiographic progression at the end of 24 months, they will remain on study, enter a Follow-up Period, and be followed until PSA or radiographic progression or initiation of non-protocol therapy. Non-protocol therapy is defined as re-initiation of hormonal therapy or initiation of other anti-cancer therapy. The total study duration is 6 years from the date of first subject enrolled once the Off-therapy Observation Period has been completed. Subjects in the Follow-up Period will be discontinued at the time of the final clinical cutoff as described in Section 11.2.2.

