11.4.2 Analytic Plan for the Secondary Endpoints

The secondary QOL endpoints will be analyzed using a similar approach as for the primary endpoint. Data up to 24 months will be included in the analysis.

PSA Modulation:

The proportion of subjects without PSA or radiographic progression and who have recovered serum testosterone to greater than 150 ng/dL at 24 months from Day 1 will be compared for subjects treated ARN-509 monotherapy vs. LHRHa monotherapy and for ARN-509 + LHRHa vs. LHRHa monotherapy. The proportions by treatment will be compared using the chi-square test or Fisher's exact test as appropriate. Results will be summarized at 24 months from Day 1 with 95% confidence intervals for each treatment arm. Subjects who withdraw from the study prior to 24 months after Day 1 will not be included in this analysis. Details can be found in the statistical analysis plan (SAP).

The proportion of subjects with a PSA less than 0.2 ng/mL after 7 months of protocol therapy will be analyzed using similar approaches for proportion of subjects without evidence of PSA or

radiographic progression during the 24-month treatment period and with recovery of serum testosterone at 24 months.

The probability distributions by treatment group of the time to PSA progression will be estimated using the Kaplan-Meier method. Durations will be measured from Day 1 of study treatment to the first date of PSA progression. The log-rank test will be used to compare the distribution of time to PSA progression.

Metabolic and Hormonal Parameters:

The mean change from baseline for markers of insulin resistance (including fasting glucose, insulin, body mass index, and hemoglobin A1C), fasting lipid panel (including total cholesterol, LDL, HDL, and serum triglycerides), and hormone levels (including DHT and estradiol) analyzed using a similar approach as for the primary endpoint.

The mean change in bone mineral density at the femoral neck, and lumbar spine as measured by DEXA scan will be compared for ARN-509 monotherapy vs. LHRHa monotherapy and ARN-509 + LHRHa vs. LHRHa monotherapy using an analysis of covariance (ANCOVA) that controls for baseline values of the corresponding measurement.

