2.1 Analysis Sets

The following analysis sets will be used for this study:

Intent-to-Treat (ITT) Population: The ITT population includes all randomized subjects and will be classified according to their assigned treatment group, regardless of the actual treatment received. Subject disposition and efficacy analyses will be performed on data from the ITT population.

Safety Population: The safety population includes all subjects who received at least 1 dose of study drug as actually treated.

Modified Intent-to-Treat Population (mITT): For outcomes related to testosterone recovery, subjects who withdrew from the study prior to 24 months after day 1 will be excluded from the analysis.

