5.3 Secondary Endpoints

The following secondary endpoints will be analyzed:

A) Quality of Life:

- Mean change from baseline in total FACT-P score over time
- Mean change from baseline in EORTC QLQ-C30/PR25 score over time
- Mean change from baseline in SHIM score over time

B) PSA Modulation:

- Time to PSA progression, which is defined as a rise to greater than 50% of the baseline serum PSA or rise of 2 ng/mL or more above the nadir, whichever is higher, confirmed by repeat measurement at least 2 weeks later (see Table 1 for the censoring rules).
- Proportion of subjects without evidence of PSA or radiographic progression during the 24-month treatment period and with recovery of serum testosterone at 24 months. Testosterone recovery will be defined as a serum testosterone greater than 150 ng/dL.
- Proportion of subjects with a PSA less than 0.2 ng/mL after 7 months of protocol therapy

C) *Metabolic and Hormonal*

- Mean change from baseline in markers of insulin resistance (including body mass index, fasting glucose/insulin, and hemoglobin A1C), fasting lipid profile, and bone mineral density as measured at the femoral neck, and lumbar spine by DEXA scan over time
- Time to testosterone recovery to greater than 50 ng/dL (non-castrate) and greater than 150 ng/dL during the off-therapy observation period for subjects randomized to the LHRHa-based treatment arms (see Table 1 for the censoring rules)
- The mean change from baseline in serum DHT and estradiol levels over time

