5.3.1.2 PSA Modulation

The proportion of subjects without PSA or radiographic progression and who have recovered serum testosterone to greater than 150 ng/dL at 24 months from Day 1 will be compared for subjects treated apalutamide monotherapy vs. LHRHa monotherapy and for apalutamide + LHRHa vs. LHRHa monotherapy. The proportions by treatment will be compared using the chi-square test or Fisher's exact test as appropriate and summarized using either risk ratio or risk difference and corresponding 95% confidence interval. Results will be summarized at 24 months from Day 1 with 95% confidence intervals for each treatment arm. Subjects who withdraw from the study prior to 24 months after Day 1 will not be included and this analysis will be conducted as modified intent-to-treat (mITT).

The proportion of subjects with a PSA less than 0.2 ng/mL after 7 months of protocol therapy will be analyzed using similar approaches for proportion of subjects without evidence of PSA or radiographic progression during the 24-month treatment period and with recovery of serum testosterone at 24 months.

The probability distributions by treatment group of the time to PSA progression will be estimated using the Kaplan-Meier method. Durations will be measured from Day 1 of study treatment to the first date of PSA progression. The log-rank test will be used to compare the distribution of time to PSA progression.

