5.3.1.3 Metabolic and Hormonal Parameters

The mean change from baseline for markers of insulin resistance (including fasting glucose, insulin, body mass index, and hemoglobin A1C), fasting lipid panel (including total cholesterol, LDL, HDL, and serum triglycerides), and hormone levels (including DHT and estradiol) analyzed using a similar approach as for the primary endpoint.

The mean change in bone mineral density at the femoral neck, and lumbar spine as measured by DEXA scan will be compared for apalutamide monotherapy vs. LHRHa monotherapy and apalutamide + LHRHa vs. LHRHa monotherapy using an analysis of covariance that controls for baseline values of the corresponding measurement.

The time to serum testosterone recovery to > 50 ng/dL and > 150 ng/dL after the cessation of protocol therapy at 12 months will be compared for apalutamide + LHRHa vs. LHRHa monotherapy. The probability distributions by treatment group of the time to testosterone recovery will be estimated using the Kaplan-Meier method. The log-rank test will be used to compare the distribution of time to testosterone recovery. Subjects who discontinue study drug prior to 12 months for disease progression, unacceptable toxicity, or study withdrawal, as well as subjects who continue hormonal therapy after 12 months or receive non-protocol therapy, will not be included in the analysis of this exploratory endpoint.

No adjustment for multiple comparisons will be made for the analysis of the secondary and correlative endpoints.

Table 1: Key censoring rules

Scenario	Censoring rule
Time to PSA Progression	
 Any increase in PSA to $> 50\%$ of the baseline value or an increase of ≥ 2 ng/mL above the nadir, whichever is higher, and confirmed by repeat measurement at least 2 weeks later is considered an event. Subjects who have no PSA progression at the time of analysis will be censored at the last known date of PSA assessment. Subjects without a baseline PSA or without any post baseline values will be censored at randomization date.

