Time to Serum Testosterone Recovery	
 Any testosterone value between 12 months to 24 months that is greater than 150 ng/dL (or 50 ng/dL as the case may be) is considered an event. If a subject had testosterone recovery (between 12 and 24 months) that happened after hormonal or subsequent therapy started, then the subject is censored at the hormonal or subsequent therapy start date. If a subject had testosterone recovery (between 12 and 24 months) that happened before hormonal or subsequent therapy started, then the recovery is considered as an event. Subjects who were not treated will be censored at randomization date. Subjects who do not fall under any of the above-mentioned category will be censored at the end of on-therapy period or off-therapy period (if the subject is in the off-therapy period).

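### SAP 2.1 words the Month-24 withdrawal exclusion so broadly that it covers time to testosterone recovery, where it contradicts Table 1's event and censoring rules

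*SAP*

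**What the plan says.** SAP 2.1 (Analysis Sets) gives the mITT rule: "For outcomes related to testosterone recovery, subjects who withdrew from the study prior to 24 months after day 1 will be excluded". The wording is plural and names no endpoint. Two endpoints fit it.

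- **The Month-24 proportion** (no progression and testosterone above 150 ng/dL at 24 months). SAP 5.3.1.2 invokes the set by name: men who withdraw early "will not be included and this analysis will be conducted as modified intent-to-treat (mITT"). Protocol 11.4.2 has the same exclusion for the same endpoint: "Subjects who withdraw from the study prior to 24 months after Day 1 will not be included in this analysis".
- **Time to recovery.** SAP 5.3 lists "Time to testosterone recovery to greater than 50 ng/dL (non-castrate) and greater than 150 ng/dL during the off-therapy observation period", for the LHRHa-based arms. SAP 5.3.1.3 gives the method: "The probability distributions by treatment group of the time to testosterone recovery will be estimated using the Kaplan-Meier method". It adds a log-rank test and does not mention mITT. Its own exclusions are men who stopped study drug before 12 months, continued hormonal therapy, or received non-protocol therapy.

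Table 1 then sets the event rule for time to recovery: "Any testosterone value between 12 months to 24 months that is greater than 150 ng/dL" (or 50 ng/dL) is an event. Recovery before later therapy is an event, recovery after it is censored at therapy start, and the remaining treated men are censored at the end of the on- or off-therapy period. SAP 5 names ITT as the population for efficacy analyses in general.

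**The concern.** A Kaplan-Meier analysis needs no completer set. A man who leaves contributes follow-up until he leaves, and a recovery seen before that is an event. Restricting the set to men still present at Month 24 selects on something known only after the event time. It discards recoveries already recorded, and it can distort the curve if leaving is connected with recovering.

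The comparison affected is combination versus LHRHa alone. Both documents look to it for evidence of adequate testosterone recovery (Hypothesis 2). The trial is open-label, so the analysis set for this comparison should be settled in writing beforehand and not chosen from several defensible readings at analysis.

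**Working it through.** **Step 1: apply each rule to the same man.** Testosterone is sampled every 2 months off therapy (SAP 2.3.3), so recovery followed by exit can be observed.

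| Man on an LHRHa arm, 12 months of therapy completed | Table 1 | SAP 2.1, literal |
|---|---|---|
| >150 ng/dL at Month 16, withdraws at Month 20 | Event at Month 16 | Deleted |
| Not recovered, withdraws at Month 18 | Censored | Deleted |

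The rules give different answers, and no section gives one precedence.

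**Step 2: size.** The plan states no event count or power for this endpoint, so there is no figure to reproduce. Inputs for an illustration:

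- 30 men per arm (SAP 1.4), all taken to enter the off-therapy year.
- Median recovery m from 16.6 weeks (16.6/4.345 = 3.82 months) to about 10 months. Protocol 6.4.2.3 cites these for higher thresholds (212 and 288 ng/dL); they serve only as a range. Recovery times are assumed exponential.
- Withdrawal share w over Months 12 to 24: not given. I assume 10% and show up to 40%. The 10% in SAP 1.4 is for FACT-P dropout or non-completion.

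*Withdrawal unrelated to recovery.* For visits g = 2, 4, ..., 12 months off therapy:

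- Recovery first seen at g: p(g) = 2^(-(g-2)/m) - 2^(-g/m)
- Still in the study at g: G(g) = (1-w)^(g/12)
- Recoveries observed per man: O = sum of p(g)G(g)
- Recoveries kept under SAP 2.1: K = (1-w) × sum of p(g)
- Share lost = (O-K)/O

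With m = 10 and w = 0.10:

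- p = 0.1294, 0.1127, 0.0981, 0.0854, 0.0743, 0.0647 (sum 0.5647)
- G = 0.9826, 0.9655, 0.9487, 0.9322, 0.9159, 0.9000
- 30 × O = 16.05 and 30 × K = 30 × 0.9 × 0.5647 = 15.25, so 0.80 recoveries are lost (5.0%)

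With m = 3.82 and w = 0.10, the sum of p is 0.8866, 30 × O = 25.46 and 30 × K = 23.94, so 1.52 are lost (6.0%).

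| w | Lost of 30 men, m = 3.82 | Lost of 30 men, m = 10 |
|---|---|---|
| 10% | 1.5 (6%) | 0.8 (5%) |
| 20% | 3.0 (12%) | 1.6 (10%) |
| 30% | 4.4 (19%) | 2.3 (16%) |
| 40% | 5.7 (26%) | 3.0 (23%) |

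A simulation with lognormal recovery (sigma 0.6) and 10% withdrawal gives 4-5% lost at a median of 6 months and 5-6% at 4 months. The 10% case is therefore about 4-6%.

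The curve itself does not shift, because under independence the chance of recovery by t given staying to Month 24 equals the unconditional chance. In the lognormal simulation the 6-month estimate was 0.504 in the reduced set against 0.500 with all men.

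*Withdrawal related to recovery.* As an extreme, let every man who withdraws have recovered first, and let R be the true proportion recovered by 12 months off therapy. The reduced set then shows (R-w)/(1-w), and the share of recoveries lost is w/R. With w = 0.10:

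- R = 0.5647: (0.5647-0.10)/0.90 = 0.516; lost 0.10/0.5647 = 17.7%
- R = 0.8866: (0.8866-0.10)/0.90 = 0.874; lost 0.10/0.8866 = 11.3%

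Kaplan-Meier with all men kept returns R in both cases.

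**The case against.** The best defence is that SAP 2.1 is merely loose. Only the Month-24 proportion invokes mITT, the protocol confines the exclusion to that endpoint, and time to recovery has its own exclusions and censoring rules, which have little purpose in a set of Month-24 completers. Specific text is usually the better guide to intent. This stands as far as it goes: the documents do not show that the deletion will be made, and a reader who infers a settled plan to delete these men goes beyond the text. It does not remove the conflict, because 2.1 is the analysis-set definition, its wording reaches this endpoint, and nothing subordinates it to 5.3.1.3.

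A reader might also infer that men removed for progression count as having withdrawn, since Protocol 3.1 says progressors "at any time during the 2 study periods will be removed from the study". That would make the loss larger and probably tie it to recovery, with a different effect in each arm. The documents do not support it. SAP 1.2, 2.2 and 5.3.1.3 list progression and withdrawal as separate reasons. The reading would also strip the Month-24 proportion of the failures it is meant to count. Any bias figure on that basis needs an assumed lag from recovery to progression in each arm, which the documents do not give.

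A further fair point is that 2.1 is not the only source of conflict. The 5.3.1.3 exclusion for non-protocol therapy would also drop men whom Table 1 treats as events or censors, so correcting 2.1 alone would leave part of the problem.

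**Conclusion.** The contradiction is real: for time to testosterone recovery, SAP 2.1 read literally deletes men whom Table 1 counts or censors, and it is broader than SAP 5.3.1.2 and Protocol 11.4.2. Taking withdrawal to mean subject or physician withdrawal, and assuming that 10% withdraw, the cost is about 4-6% of observed recoveries, or roughly one or two men per arm of 30. Bias is small unless withdrawal is related to recovery. The loss grows with the withdrawal rate, which is an assumption throughout. The endpoint is secondary, is called exploratory in 5.3.1.3, and has no multiplicity control; the primary FACT-P analysis is untouched. It should be corrected because the stated rule discards observed events and the correction is cheap.

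**What to change.** 1. In SAP 2.1, limit the mITT set to the Month-24 proportion in 5.3.1.2, as Protocol 11.4.2 does.
2. In SAP 5.3.1.3, state that the Month-24 withdrawal exclusion does not apply to time to recovery. Among LHRHa-arm men who meet the 12-month therapy condition already there, a recovery observed before leaving is an event at its date, and a man who leaves unrecovered is censored at his last testosterone sample. Table 1 currently censors at the end of a period and does not name that date.
3. In the same edit, reconcile the exclusion of men who receive non-protocol therapy with Table 1, which counts recovery before later therapy as an event and otherwise censors at therapy start.

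Items 1 and 2 are SAP wording only; the samples are already scheduled and the method already specified. For item 3, Protocol 11.4.2 carries the same exclusion. If Table 1's rule is kept, the protocol sentence must be aligned or the departure recorded.

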2.2 Study Period I: On-therapy Period (Months 1-12)

The 24-month study treatment period will be divided into two 12-month periods: the on-therapy period during which subjects receive protocol therapy (apalutamide monotherapy, apalutamide + LHRHa, or LHRHa monotherapy). Subjects will commence protocol therapy on Day 1 of the on-therapy period. The study timeline is defined as Day 1 = first dose of study treatment. Subsequent study time points will be defined based on study calendar, irrespective of subsequent dose delays/interruptions.

Subjects will be treated with protocol therapy for 12 months, or until disease progression (either by PSA or radiographic), unacceptable toxicity, subject/physician withdrawal, or initiation of non-protocol therapy. PSA progression is defined as an increase in PSA to > 50% of the baseline value or an increase of > 2 ng/mL above the nadir, whichever is higher confirmed by repeat measurement at least 2 weeks later. Radiographic progression is defined as the detection of new metastasis on either bone scan or cross-sectional imaging (CT or MRI) [5]. If subjects develop progressive disease (either by PSA or radiographic) while receiving protocol therapy, they will discontinue protocol therapy, have a Progression Visit, and be treated as per individual investigator discretion.

If there is no evidence of disease progression (by serum PSA or radiographically) after 12 months of protocol therapy or if subject discontinues treatment before 12 months of protocol therapy for reasons other than disease progression, subjects will enter the 12-month Off-therapy Observation Period. Continuation of hormone therapy or initiation of any form of anti-cancer

therapy in the absence of PSA or radiographic progression will be considered non-protocol therapy and will result in study removal.

Efforts will be made to ensure that subjects who develop progressive disease before 12 months of therapy still complete QOL scales at 3 and 12 months.

2.2.1 Day 1 of Study Treatment

Patients will return to study site for a history and physical exam including weight, measurement of serum PSA, and dispensing of study drug(s), including the first injection of LHRHa and 1-month supply of apalutamide for subjects randomized to those arms. Collection of optional samples (samples for banking, archival FFPE blocks or slides for transcriptome profiling (RNAseq), whole blood for RNA testing, and plasma for biomarker testing) should occur before pre-dose.

2.2.2 LHRH Agonist

For subjects randomized to either the LHRHa monotherapy or the LHRHa + apalutamide combination treatment arms, the choice and schedule of LHRHa will be up to individual investigator's discretion and will be administered for a total of 12 months of therapy in the absence of disease progression or unacceptable toxicity. No change in dosing schedule of LHRHa will be permitted once the subject has commenced protocol therapy. For example, the use of every 3 month subcutaneously injected LHRHa would be administered on Day 1 and on Months 3, 6, and 9. The use of LHRH antagonists (ie, degarelix) will not be permitted. No dose reductions or interruptions of LHRHa will be permitted. If a subject does not receive a scheduled LHRHa injection within ± 7 days of the scheduled due date for injection, he will be removed from study. Subjects on the LHRHa monotherapy arm will not be allowed to crossover to receive apalutamide.

2.2.3 Apalutamide

Subjects randomized to either of the two apalutamide-containing arms will receive apalutamide dosed orally on a daily basis with or without food. The starting dose of apalutamide is 240 mg/day. With Amendment 7 (Version 8.0), subjects who are receiving the soft gel capsules will switch to the tablet formulation. Ongoing subjects on a reduced dose of capsules should continue with that dose with lowest allowed dose being 120 mg. Dose delays and dose reductions will be permitted as per guidelines outlined in the study protocol/

2.2.4 Safety Assessment

Subjects will be assessed for adverse events at each monthly clinic visit during the On-therapy Period. Adverse event collection starts with the signing of the ICF. Adverse events will be graded according to the National Cancer Institute (NCI)-Common Terminology Criteria for Adverse Events (CTCAE) Version 4.03 (available at <http://ctep.cancer.gov>). See the study protocol for attribution of adverse events. Dose modifications (interruptions, reductions or both) for apalutamide, will be allowed as per guidelines outlined in the study protocol.

